#### *Study secondary endpoints*

1. Healing time (in which healing is represented by a lasting and complete re-epithelialization);
2. Reduction of the lesion surface in both arms, during the 20 weeks, measured in absolute terms (square centimeters) and as % of the initial size;
3. Quality of life (QoL), evaluated both with specific questionnaires (EuroQoL-5D) and generic questionnaires (Wound-QoL);
4. Perception of pain measured with a subjective analogue rating scale (VAS);
5. Assessment of the costs related to the two arms in the perspective of the National Health System, NHS (considering only direct health costs) and in the perspective of the Society (considering beyond direct health costs, direct non-health costs and indirect costs);
6. Patient's satisfaction with the EmoLED therapy, assessed by administering specific questionnaires;
7. Appreciation, complexity and usefulness of the EmoLED therapy by the operators assessed through the administration of specific questionnaires;
8. Security of treatment (number of Adverse Events in the two groups);
9. Evaluation of the cost-effectiveness of using EmoLED for the treatment of ulcers.

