In case, therefore, the lesion presents signs of infection as described above, the patient will interrupt their presence in the study and will be treated adequately. The patient can continue the study only if there is a remission of the symptoms of infection. The event will be reported in the appropriate section of the Data Collection Form.

The patient will be invited to a scheduled check-up at the referral center to assess the progress of the lesion, once every 30 days, or as needed.

The patient, if the wound healing occurs while being managed at home, will be invited to return for a check-up visit at the referral center within a week, to confirm the healing.

If at the conclusion of the participation of the patient in the clinical investigation, any additional treatments are required to those normally provided for the clinical condition considered in this study, the sponsor will cover the costs incurred for such treatments.

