### **Measurable parameters**

Following enrollment and signature of the informed consent, during the first visit / treatment, at the reference outpatient center, the salient data and photographic images of the lesion of each patient will be collected in the appropriate data collection form (see Annex).

During the home visits, twice a week (concomitantly with the dressing change and with the treatment with EmoLED for the Treated Group, respectively), photographic images of the lesion of each patient, some clinical data and the perception of pain through VAS scale will be collected. These variables will be measured at each

visit or until healing. During the visits (to be scheduled at least once every 30 days) carried out at the reference center participating in the trial, the clinical data on the Data Collection Form (see Annex), the photographic images of the lesion of each patient, pain perception using the VAS scale and quality of life data will be collected.

Questionnaires relating to the Quality of Life Section will be administered at the first visit and at the last visit. In particular, standard tools such as the generic questionnaire EQ-5D and the specific questionnaire Wound-QoL will be administered, both available and validated in Italian.

The parameters used that will be found for the definition of the result in the study are:

- Re-epithelialization of the lesion / reduction of the lesion area through data collection form and photographic images of the lesions treated with EmoLED and control lesions (Annexes B, C);
- Intensity of pain perceived by the patient through the VAS scale (Annexes B, C);
- presence of infection (Annexes B, C);
- Level of quality of life perceived by the patient through a questionnaire on the quality of life (EuroQoL and Wound-QoL) (Annexes D, E);
- Appreciation of the therapy (patient) through a specific questionnaire to be filled in by the patient (Annex F);
- Satisfaction, complexity and usefulness of using the device (operator) through a specific questionnaire to be filled in by the operator (Annex G);
- Direct and indirect costs (Annexes H, I);
- Detection of Adverse Events (Annexes B, C).

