#### *Registration of clinical data*

The data related to the evaluation of the study endpoints are acquired, for both groups, during the visits.

The parameters of the Data Collection Form, the questionnaires about quality of life and the questionnaire about the acceptability of the therapy are acquired during the outpatient visit at the reference centre and kept on paper for the clinical trial length, and conserved in both paper and digital form; the pictures of the lesion are acquired and kept in digital form, during the length of the clinical trial and afterwards.

The storage coding follows the patient recruitment code and acquisition timing.

During each visit, a picture of the lesion will be taken and analyzed so that the process of healing can be valued in a quantitative and qualitative way.

At each visit, data on the patient's perception of pain will also be collected.

The Quality of Life related questionnaires will be administered at the first visit and at the last visit, scheduled after 24 weeks, at the reference center. In particular, standard tools such as the generic EQ-5D questionnaire, validated in Italian, will be administered. Similarly, the questionnaire for the patient acceptance of the therapy (generic for both the group treated with EmoLED and the control group) will be administered at the

last visit, scheduled after 24 weeks, or on the date of recovery. The operator satisfaction questionnaire (to be administered exclusively to staff belonging to Home Care) will be administered at the end of the study.

*Data collection form (screening period) (Annex A)*

The collection of data relating to the Clinical Section includes the patient's identification code, date of birth, sex and characteristics of the lesion in question. There is also a space for any concomitant pathologies, any drug therapy (to be registered in terms of active substances). The last section is intended for recording the size of the wound.

*Data collection form (Research Center) (Annex B)*

The collection of data relating to the Clinical Section includes the patient identification code, date of birth, sex and characteristics of the lesion to be collected in the initial phase. There is also a space for any concomitant pathologies, any drug therapy (to be registered in terms of active substances), any notes.

The second part of the form is organized as a matrix where the row represents the measurable parameters for each time of observation (reported in column).

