### **Statistical analysis**

Demographic and clinical data will be presented in tables and graphs in the form of frequencies and percentages for categorical variables, mean, standard deviation, median and interquartile range for continuous variables, differentiating by reference population and treatment group.

In the first analysis a qualitative comparison between the treatment groups will be carried out (healed/not healed) through the test  $\chi^2$  or the exact test of Fisher in the case of counts of less than 5. The results will be presented in contingency tables and bar charts.

A quantitative comparative statistic between treatment groups will then be performed by comparing the percentage reduction in the area of injury, the variation in quality of life level (QoL) and the variation in pain perception (VASS) through Mann-Whitney's nonparametric test.

The choice to perform a non-parametric analysis lies in the low sample size and therefore it is preferred to have more conservative significance values. The results will be presented in tables with median and interquartile interval in the two groups with its p.value and graphically through the box plot.

To analyze the internal and time-related differences between groups, Friedman's non-parametric test for the outcome variables will be performed.

Generalized linear models (GLM) will be used to investigate whether differences between the two groups are influenced in a confusing way by demographic, clinical covariates, pre-treatment measurement, and to measure their impact which will allow us to understand which variables they include on the outcome and will also allow us to analyze the differences between the equal groups of these covariates.

For the comparison about recovery time, since the study is based on the principle of "intention to treat" and therefore there is no caesura, it will be performed by comparing the average recovery times through the non-parametric test of Mann-Whitney.

Then a descriptive statistic will be made through tables with frequencies and percentages, and bar charts of the treatment satisfaction indices in patients and operators. In addition, adverse events in both groups will be described, if present.

Due to the generally asymmetric nature of the cost distribution, the comparison of the costs associated with the two treatment arms, both from the perspective of the SSN and the Company, will be carried out using the non-parametric U test of Mann-Whitney.

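### Friedman's test is given the between-group time course, but it has no treatment term and cannot compare the arms over time

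*Protocol*

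**What the plan says.** The protocol's Statistical analysis section lists the comparisons in turn. Healed or not healed is compared by chi-square or Fisher's exact test. Next: "A quantitative comparative statistic between treatment groups will then be performed by comparing the percentage reduction in the area of injury", together with change in quality of life and in pain, by Mann-Whitney. For time to healing, "it will be performed by comparing the average recovery times through the non-parametric test of Mann-Whitney". Costs are also compared by Mann-Whitney. Generalised linear models are added for covariates and the pre-treatment measurement.

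One sentence deals with time: "To analyze the internal and time-related differences between groups, Friedman's non-parametric test for the outcome variables will be performed".

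The repeated outcomes are lesion area and VAS pain. Both are recorded at the twice-weekly home visits and at the centre check-ups, which take place "once every 30 days, or as needed" (Medical-surgical procedures and study follow up). Reduction of lesion surface over the 20 treatment weeks, in both arms, is a secondary endpoint.

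Quality of life is less clear. One sentence of Measurable parameters includes it in the 30-day centre visits ("pain perception using the VAS scale and quality of life data will be collected"). The next paragraph fixes it at two points ("Questionnaires relating to the Quality of Life Section will be administered at the first visit and at the last visit"), and Registration of clinical data agrees ("administered at the first visit and at the last visit, scheduled after 24 weeks").

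**The concern.** The sentence names its purpose, a difference between groups over time, and assigns a test that has no group factor. Friedman's test is made for repeated measurements on the same subjects. Here the two arms consist of different patients, so the arm is a between-patient factor that the test does not contain. Run per arm, it says whether each arm changed. Setting one arm's p-value against the other's is not a test of the difference.

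Lesions under standard care with offloading can be expected to shrink in both arms. A Friedman test would then probably be significant whatever the device does, and the protocol's wording invites that result to be read as a time-related difference between groups. The protocol describes the trial as a proof of concept whose results may help to size later studies, so a misattributed time course could carry forward.

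**Working it through.** **Inputs from the protocol.** Two parallel arms, 1:1, 20 patients each; 24 weeks of follow-up; centre visits every 30 days; significance at p < 0.05 (sidedness not stated, two-sided assumed). The sample size was set on recruitment capacity, so there is no power figure to reproduce.

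**Number of centre visits.** 24 × 7 = 168 days, and 168 / 30 = 5.6. That gives baseline plus five visits, six in all, or seven if the week-24 last visit is counted separately.

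**The statistic.** With n patients and k visits, rank each patient's k values from 1 to k and let R_j be the sum of ranks at visit j. Without ties,

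Q = 12 / [n k (k + 1)] × Σ R_j² − 3 n (k + 1), referred to chi-square on k − 1 degrees of freedom.

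The arm appears nowhere. Two consequences follow without any assumed effect:

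- Shuffling arm labels cannot change Q. On one simulated data set of 40 patients and six visits, 1,000 shuffles all gave 121.96.
- Adding a constant to every value in one arm cannot change Q. On a second data set Q was 3.214 both before and after adding 5 SD to one arm.

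**Simulation A: general behaviour.** Assumed: 20 per arm, seven visits, normal data with SD 1, within-patient correlation 0.5, linear trends, 2,000 runs.

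| Situation | Pooled Friedman significant | Mann-Whitney on patient slopes significant |
|---|---|---|
| Same decline of 1.5 SD in both arms | 100% | 5% |
| Opposite trends of 1 SD | 1.6% | 100% |
| Flat courses, constant 2 SD gap between arms | 5.4% | 5.4% |

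In the third row there is no difference in slope, so 5.4% is the expected error rate for the slope test. Friedman run separately in each arm, with the same 0.6 SD decline in both, was significant in one arm only in 47% of trials (38% at 0.7 SD, 26% at 0.8 SD). A contrast of per-arm p-values would therefore often suggest a difference where none exists.

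One layout does bring the arm in: visits as blocks and arm medians as cells. It breaks the independence of blocks. With identical arms it rejected in 16–30% of trials at a nominal 5% (six or seven visits, within-patient correlation 0.5–0.7).

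**Simulation B: healing curves.** Assumed: log area with residual SD 0.3, baseline SD 0.5 and slope SD 0.1; below 10% of initial area counted as healed and set to zero from then on; 1,000 runs per case. Control means at visits 1–5 were 82, 67, 55, 45 and 37% of initial area. For an earlier decline, the treated means were 61, 45, 37, 34 and 31%. Steady divergence used −0.2 against −0.3 per visit on the log scale. The group-by-time test is the rank-based ANOVA-type interaction statistic.

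| Six-visit case | Friedman (per arm and pooled) | Group-by-time, with / without baseline | Mann-Whitney at visits 1–5 |
|---|---|---|---|
| Identical arms | 100% | 4.9% / 5.1% | 4.0–5.4% |
| Earlier decline, treated | 100% | 67.8% / 29.9% | 53.1, 72.3, 63.0, 30.2, 13.4% |
| Steady divergence | 100% | 49.9% / 35.9% | 11.4, 25.3, 43.4, 54.2, 61.5% |

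With seven visits the group-by-time test gave 4.0% / 4.4% for identical arms and 78.9% / 59.9% for the earlier decline. Friedman again gave 100% in both.

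**What else could fill the gap.** The Mann-Whitney tests compare change scores and are tied to no visit. The regression models are described by covariates and confounders, with no time term, arm-by-time term or patient effect. No analysis in the section tests the time course between arms.

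**The case against.** The protocol reads as a translation, and the sentence may have meant change over time inside each group. For that, Friedman per arm is correct, and its place after the between-arm Mann-Whitney tests supports the reading. This rescues the within-group half of the sentence. The words still say between groups, so they need changing on either reading.

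No listed endpoint strictly requires an interaction test. Area reduction, pain and healing time each have a two-group test, and a Mann-Whitney at an intermediate visit could show an early difference. This stands and keeps the scope small. But a protocol that names an unsuitable test for a stated purpose has made a misstatement, which differs from leaving a detail to an analysis plan.

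The simulations rest on assumed curves, and the 100% follows from letting lesions shrink. VAS pain was not simulated. That is fair. The argument rests on the formula, and the simulations only illustrate it.

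On the percentage scale the baseline is 100 for every patient, and including it accounts for much of the group-by-time test's power (67.8% against 29.9%). This also stands, although the error rate stayed near 5% with that column included. In a re-run of the earlier-decline case, a Mann-Whitney on each patient's mean over visits gave 59%, against 66% for the rank interaction test and 70% for Mann-Whitney at visit 2. No power gain over a well-chosen Mann-Whitney is claimed.

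Finally, restricting the test to centre visits leaves out the home measurements. That is a real loss of data, but under Study design the centre evaluator is the one kept unaware of allocation.

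**Conclusion.** The concern holds. Friedman's test does not contain the arm and cannot answer the question the protocol gives it. This follows from the form of the statistic and needs no assumed effect. The rejection rates depend on the assumed curves, SDs and number of visits and are illustrative only.

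The defect is confined to the between-group time course of lesion area and VAS pain. The primary endpoint, the comparisons of change, healing time and costs are not touched. For quality of life, if the two-point schedule applies, there is no course to compare beyond the change score already tested. The sentence should be corrected before analysis, but it does not threaten the trial's main result.

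**What to change.** Replace the sentence by two or three that do the following:

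- Limit Friedman's test to describing change over the centre visits within each arm, and state that its p-values will not be compared between arms.
- For the between-group time course of percentage of initial area and of VAS pain, name one test with a group-by-time term. A rank-based ANOVA-type test over the centre visits, including baseline, keeps the plan's non-parametric choice.
- Enter confirmed healed lesions as zero area, and label the result exploratory.

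No new data, visits or patients are needed. The cost is a little more analysis work and a result expressed as relative effects, not square centimetres. Power with 20 per arm may be low: 30–79% in the assumed early-decline cases and 36–50% under steady divergence. A non-significant result should not be read as showing equal courses.

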#### **Endpoints**

##### *Study primary endpoint*

The primary endpoint of the study will be the percentage of lesions considered healed (meaning as having a lasting and complete re-epithelialization) in the two groups at the twenty-fourth week of observation.

Healing must be confirmed by the Principal Investigator or their staff during an outpatient visit at the reference center participating in the study; the date of the recovery will in any case be indicated as the one of the first response, if it had occurred before the last visit to the reference center.

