#### **Study design**

The study is a double-blind pilot trial on outpatient patients, followed in an integrated way at a specialized center for the care of diabetic foot and Home Care as territorial home nursing service, articulated over a total period of 24 weeks (20 weeks of treatment plus 4 weeks of observation). Therefore, after an initial characterization and treatment setting by the specialist center, the patients will be followed biweekly by the nurses of Home Care, to then be re-evaluated at the center on a monthly basis.

The assessment of the evolution of the lesions will be made at the specialist center, in which the evaluating physician will not be aware of the type of home treatment performed by the patient and its allocation group and the execution of treatment with EmoLED will be performed ensuring the blindness also to the patient. This also ensures an adequate level of masking to ensure that the study is double-blind.

Both for the treatment group and for the control group, the patient will not be aware of the group to which he has been assigned; the operator will make the patient wear glasses (distributed to each patient at the beginning of the study) totally obscuring and will take out of the room any family members or other people before performing/simulating the treatment with the EmoLED device. In case the patient has been assigned to the control group, the operator will simulate to perform the treatment, turning on the device but pointing the light beam away from the patient (e.g. illuminating the floor).

Once the inclusion criteria are verified and the patient has given their consent to participate in the study, a two-week pre-enrollment period will be observed, in which the patient will receive standard treatment (as

indicated below); at the end of the two weeks of pre-enrollment, the patient will be re-evaluated to see if the lesion has not reduced by 50% with standard treatment alone.

If so, the patient will leave the study while, if the lesion has not reached this percentage of re-epithelialization, the patient will be randomized into the two study groups: the control group will continue with only the standard treatment as described above, while the treatment will receive in EmoLED treatment in addition to the standard treatment.

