#### **Known or predictable factors that may compromise the results and their interpretation**

An incorrect recording of photographic images does not make it possible to determine the area of the lesion via software. This problem is tackled by providing precise instructions on the correct use of the tools available for the retrieval of images.

Discontinuity of patients regarding adherence to plantar offloading can affect recovery times. Before recruiting a patient, the doctor ensures that the patient is available to follow the prescribed therapy and to go to the clinic when required.

In case the patient misses a check-up visit, this can be regained within two days following the scheduled date. If this is not possible, the visit will not be carried out and the patient will be evaluated at the next visit. If the patient misses more than one visit, they will be excluded from the study (drop out).

Other reasons why patients will have to leave the study early are the lack of treatment, with EmoLED or with standard therapy, for more than four consecutive times, or for the lack of a quarter of home visits in total (unless non-treatment is provided for in this Protocol, such as in the case of suspension due to infection). Patients in which it is not possible to establish the exact date of recovery for various reasons, and patients who, in the opinion of the investigator, show a poor compliance with the therapeutic standards required by the study protocol, will also be excluded.

In such cases, the investigator will exclude patients from the study, recording on the data collection form, in addition to the date of exclusion, also the reasons why the patient was excluded.

The patient may, however, withdraw from the study at any time without having to give any explanation to the investigator (withdrawal of consent).

Following the exclusion or abandonment of the study by the patient, the data collection form is identified, scanned and stored.

If a patient withdraws from the study, the Principal Investigator records the event in the identification register and on the data collection form and stores it all.

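### Intention-to-treat does not remove censoring: lesions unhealed at week 24 and early leavers have no recovery time, so the planned comparison of average recovery times is not defined

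*Protocol*

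**What the plan says.** Secondary endpoint 1 is "Healing time (in which healing is represented by a lasting and complete re-epithelialization"). For its analysis, the Statistical analysis section starts from the intention-to-treat principle and continues: "and therefore there is no caesura, it will be performed by comparing the average recovery times through the non-parametric test of Mann-Whitney".

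Other sections bear on whether every patient can have such a time:

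- Study primary endpoint: the "percentage of lesions considered healed (meaning as having a lasting and complete re-epithelialization) in the two groups at the twenty-fourth week of observation". On dating, "the date of the recovery will in any case be indicated as the one of the first response", with healing confirmed at the reference centre.
- Study design: follow-up is "articulated over a total period of 24 weeks (20 weeks of treatment plus 4 weeks of observation").
- Medical-surgical procedures and study follow up: if the wound becomes infected, "the patient will interrupt their presence in the study and will be treated adequately". The patient may continue only if the infection remits.
- Known or predictable factors: patients leave for "the lack of treatment, with EmoLED or with standard therapy, for more than four consecutive times", for more than one missed visit, or for missing a quarter of home visits. Those whose exact recovery date cannot be established, and those who in the investigator's opinion "show a poor compliance with the therapeutic standards required by the study protocol, will also be excluded".
- Management of missing data: non-completers stay in the analysis under intention-to-treat, with last observation carried forward. For skipped visits, the mean of the adjacent visits may be used instead.

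**The concern.** The sentence uses a rule about the analysis population to settle a question about observation. Intention-to-treat keeps each patient in the assigned arm. It does not tell us when a lesion healed if nobody saw it heal. Keeping non-completers in the analysis adds patients with incomplete times.

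Because the protocol assumes the problem away, it never says what value an unhealed patient takes. Three analyses fit the wording: healers only, time of exit used as recovery time, or week 24 for everyone not seen to heal. They behave very differently, and the choice could be made after the data are seen. The Sample number section says the results may be used to size later studies, so a distorted healing-time difference could carry over into their planning.

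**Working it through.** **The premise against the rest of the protocol.** The primary endpoint is a percentage healed at week 24, and the first planned test compares healed with not healed. Both presume that some lesions stay open. Recovery is dated at first response, so an open lesion has no date, and observation stops at week 24. Carrying forward the last observation of an open lesion yields its area or the status not healed; neither is a time.

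**Inputs.** From the protocol: 20 patients per arm, follow-up of 24 weeks, significance at 0.05 (two-sided assumed). The protocol has no power calculation or healing rate to reproduce. Assumed: exponential healing; control proportion healed by week 24, p0, of 30%, 50% or 70%; hazard ratio HR of 2 or 1.5.

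**Formulas.** Hazard λ = −ln(1−p)/24. Treated proportion p1 = 1 − (1−p0)^HR. Patients without a time = 20(1−p0) + 20(1−p1). Mean time among healers = 1/λ − 24(1−p)/p. Restricted mean to week 24 = p/λ.

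**Example, p0 = 50%, HR 2.** λ0 = 0.6931/24 = 0.02888, so 1/λ0 = 34.62. p1 = 1 − 0.25 = 75% and 1/λ1 = 17.31.

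- Without a time: 10 + 5 = 15 of 40.
- Healers' means: 34.62 − 24 = 10.62 and 17.31 − 8 = 9.31; difference 1.31 weeks.
- Restricted means: 0.5 × 34.62 = 17.31 and 0.75 × 17.31 = 12.98; difference 4.33 weeks.

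| HR | p0 | Without a time (of 40) | Healers-only difference (weeks) | Restricted-mean difference (weeks) |
|---|---|---|---|---|
| 2 | 30% | 23.8 | 0.70 | 3.03 |
| 2 | 50% | 15.0 | 1.31 | 4.33 |
| 2 | 70% | 7.8 | 2.05 | 4.88 |
| 1.5 | 30% | 25.7 | 0.35 | 1.60 |
| 1.5 | 50% | 17.1 | 0.67 | 2.39 |
| 1.5 | 70% | 9.3 | 1.08 | 2.85 |

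The last two columns are different estimands. Only the restricted mean compares the arms as randomised.

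**Power at HR 2**, by simulation with 10,000 runs per cell, for p0 = 30/50/70%. The drop-out row takes 25% per arm, independent of healing. That is an upper assumption, because the 25% in the Sample number section also counts denials.

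| Drop-out | Mann-Whitney, healers only | Mann-Whitney, unhealed at 24 weeks | Log-rank |
|---|---|---|---|
| None | 4/7/14% | 26/38/43% | 28/41/50% |
| 25% per arm | 4/7/12% | 23/32/38% | 25/37/47% |

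**Type I error with no true difference.**

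- *Exit time used as recovery time.* With 40% healed in both arms and independent drop-out of 10% against 40%, this gives about 18%. Log-rank gives about 5%, and ranking the unhealed last about 6%.
- *Log-rank when exits are unrelated to healing.* It stays at 5–6% with no drop-out or with 10% against 30%.
- *Exits only among patients who would not heal by week 24, 10% against 30% of those randomised.* Log-rank gives 6.1/7.0/10.6%. The 50% figure rises to about 10% if the number of leavers per arm is fixed rather than random; at 70% every non-healer in one arm leaves, an extreme case. Mann-Whitney with the unhealed at 24 weeks gives 4.9/4.6/4.8%, and with exit time used as recovery time about 14–19%.
- *The same with 10% against 20%.* Log-rank gives 5.5/5.8/6.8%; Mann-Whitney with the unhealed at 24 weeks gives 5.1/4.8/4.9%.

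**The case against.** The sentence invokes intention-to-treat and the missing-data section keeps non-completers, so the authors probably meant every patient to have a value, and the healers-only figures describe the reading the text favours least. If that value is 24 weeks, Mann-Whitney holds its level and loses only 2–9 points of power to log-rank. Even that loss depends on proportional hazards: with an assumed early effect (HR 3 to week 8, then 1, no drop-out) Mann-Whitney gives 21/39/61% against 19/33/55% for log-rank. Log-rank is also the more exposed of the two when leaving is related to prognosis. Infection is described as an interruption, not necessarily an exit. The exclusion rule can be read as governing participation and the missing-data rule as governing analysis. This is one secondary endpoint in a 40-patient pilot that claims no power.

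Much of this stands. Mann-Whitney is not wrong in itself, and neither test is better in all circumstances, which is why both belong in the plan. What does not stand is that the text already supplies the 24-week rule. It states that there is nothing to handle, and carrying forward could equally lead an analyst to exit time, which can inflate type I error. A patient whose infection does not remit does leave. If exclusion is meant to end participation only, the protocol should say so.

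**Conclusion.** The concern holds. The protocol states a false premise and fixes an analysis on it, so this is not a detail left to a statistical analysis plan: a plan that followed the sentence would inherit the error, and one that censored would contradict it. Reading caesura as censoring is an inference, but it is the only meaning that fits.

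The size depends on the reading taken. Healers only discards the randomised comparison and nearly all power; exit time can push type I error to about 14–19%; week 24 for all unhealed patients is close to adequate. All figures rest on assumed healing and drop-out rates. The damage is confined to healing time, and the primary test is untouched. It should be fixed, but it does not threaten the trial's main result.

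**What to change.** In Statistical analysis, delete the statement that there is no censoring and replace the comparison of average recovery times with the following:

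1. Analyse time from randomisation to healing in all randomised patients by Kaplan-Meier and log-rank, with the hazard ratio and its 95% confidence interval. Censor unhealed patients at week 24 and leavers at their last lesion assessment.
2. Report the restricted mean time to week 24 per arm and the difference, which does not rely on proportional hazards.
3. Because exits for infection, missed treatment or poor compliance may be related to prognosis, add one sensitivity analysis: Mann-Whitney with every patient without observed healing set to a tied worst value of 24 weeks.

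Separately, reconcile the exclusion of patients without an exact recovery date with the intention-to-treat rule. Keep them in this analysis, dated at the first visit at which complete closure was recorded, with the centre's confirmation of healing still required.

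The cost is one rewritten paragraph and one cross-reference in the section on factors that may compromise the results. No new data are needed, and standard R survival functions suffice. The interval will be wide: log-rank power is about 25–50% at HR 2 under the assumed rates. Log-rank is valid only if leaving is independent of healing, hence the sensitivity analysis.
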